### 8.3. Exploratory Immunogenicity Analyses

ChAd68-specific neutralization will be analyzed in a similar manner as the pseudovirus and live neutralization, for participants who received the ChAd-S and ChAd-S-TCE vaccines (Groups 1, 13, 14, and 15) at Study Days 1 and 29.

Memory B cell responses to ChAd-S or ChAd-S-TCE and SAM-S or SAM-S-TCE will be analyzed in a similar manner as the T cell assays with tables showing the mean with 95% CI, median, min, and max and figures illustrating the distribution of responses over time.

## 9. SAFETY EVALUATION

Summaries and analyses of safety data will be presented for the safety analysis population.

Solicited non serious AEs will be collected from the time of each vaccination until 7 days after. Solicited AEs will be summarized by severity for each day post each vaccination and as the maximum severity over all 8 days. Additionally, solicited AEs will be analyzed using standard techniques, such as 95% CIs (using the Clopper-Pearson method), to summarize the proportion of participants reporting each symptom, any local (vaccination site) symptom, and any systemic symptom.

### 9.1. Demographic and Other Baseline Characteristics

Summaries of sex, ethnicity, race, age, weight, BMI, previous COVID-19 infection, previous COVID-19 vaccinations (where applicable), and time from most recent community COVID-19 vaccination (where applicable) will be presented by vaccination arm and overall (starting with [Table 37](#) and ending with [Table 46](#)). Ethnicity is categorized as Hispanic or Latino, or not Hispanic and not Latino. In accordance with NIH reporting policy, participants may self-designate as belonging to more than one race or may refuse to identify a race, the latter reflected in the CRF as “No” to each racial option. Summary clinical laboratory values and vital signs at baseline will be included in tables grouped by vaccination arm and overall (beginning with [Table 312](#) and ending with [Table 336](#)).

Individual participant listings will be presented for all demographics ([Listing 6](#)). Baseline clinical laboratory values will be included in [Listing 12](#) and [Listing 13](#), baseline vital signs will be included in [Listing 14](#), and baseline physical exam findings will be included in [Listing 15](#).

#### 9.1.1. Prior and Concurrent Medical Conditions

Complete medical history is obtained by interviewing participants at first study visit, and interim medical history will be collected at follow-up visits. Medical history is limited to significant medical disorders of the head, eyes, ears, nose, throat, mouth, cardiovascular system, blood, lymph nodes, endocrine system, lungs, gastrointestinal tract, liver, pancreas, musculoskeletal system, skin, and genital/reproductive tract. A history of any allergies, clotting or other abnormality of the coagulation system, cancer, immunodeficiency, psychiatric illness, substance abuse, and autoimmune disease are solicited.

All current illnesses and past pre-existing medical conditions will be MedDRA coded using MedDRA dictionary version 23.0 or higher. Summaries of participants’ pre-existing medical conditions will be presented by vaccination arm and overall ([Table 47](#), [Table 48](#), [Table 49](#), [Table 50](#), and [Table 51](#)). Individual participant listings will be presented for all medical conditions ([Listing 7](#)).

#### 9.1.2. Prior and Concomitant Medications

Administration of any medications, therapies, or vaccines will be recorded. Concomitant medication includes all current medications and medications taken in the 30 days prior to signing of the ICF for the duration of the study. Medications reported are limited to those taken within 30 days prior to the first study vaccination and for 12 months after the last study vaccination.

Summaries of medications that were started prior to dosing and continuing at the time of dosing will be presented by WHODrug Terms 2 and 3 and vaccination arm ([Table 337](#), [Table 338](#), [Table 339](#), [Table 340](#), and [Table 341](#)).

Individual participant listings will be presented for all concomitant medications ([Listing 16](#)).

## 9.2. Measurements of Treatment Compliance

All participants are to receive one or two doses of the study product administered in the clinic. Section 7 of the protocol provides summaries of key treatment compliance milestones/variables. The number of participants receiving each dose will be summarized as part of the participant disposition table. The month of first study vaccination will be tabulated by vaccination arm and overall ([Table 30](#), [Table 31](#), [Table 32](#), [Table 33](#), [Table 34](#), and [Table 35](#)). Individual participant listings will be presented for all participants terminated early or discontinued treatment ([Listing 2](#)). Listings will be presented for all participants-specific and non-participant specific protocol deviations ([Listing 3](#) and [Listing 4](#)).

## 9.3. Adverse Events

All adverse events reported will be included in the summaries and analyses. When calculating the incidence of adverse events (i.e., on a per participant basis), each participant will only be counted once and any repetitions of adverse events within a participant will be ignored; the denominator will be the total population size.

Overall summaries of adverse events are presented by vaccination arm beginning with [Table 212](#), [Table 213](#), [Table 214](#), [Table 215](#), and [Table 216](#). Adverse events occurring in at least 5% of participants in any vaccination arm by MedDRA SOC and preferred term are presented by vaccination arm beginning with [Table 217](#), [Table 218](#), [Table 219](#), [Table 220](#), and [Table 221](#).

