#### Adverse Events

AE means any untoward medical occurrence associated with the use of an intervention in humans, whether or not considered intervention-related [21 CFR 312.32 (a)]. An AE can therefore be any unfavorable and unintended sign, symptom or disease temporally associated with the use of medicinal (investigational) product.

Any medical condition that is present at the time that the participant is screened will be considered as baseline and not reported as an AE. However, if the severity of any pre-existing medical condition increases, it will be recorded as an AE.

AEs can be further divided into solicited AEs and unsolicited AEs. Solicited AEs are those that are described in the package insert as local or systemic reactogenicity occurring in the first 7 days after vaccination. Unsolicited AEs are those events that the participant reports occurring without being queried about the specific event.

AEs will be assessed for severity and relationship to study intervention. Reporting of all AEs, solicited and unsolicited, will occur during the period from study product administration on Day 1 through 28 days after each vaccination. After 28 days post last vaccination through the end of study, only SAEs, protocol specified AESIs (including PIMMCs, MAAEs, and NOCMCs), and AEs leading to withdrawal from the study will be reported.

All AEs, solicited and unsolicited, will be captured on the appropriate DCF. Solicited AEs will be regarded as related to the study product and will not require separate entry into the AE log. Information to be collected for unsolicited AEs includes event description, date of onset, assessment of severity, relationship to study product and alternate etiology (assessed only by those with the training and authority to make a diagnosis and listed on the Form FDA 1572 as the participating site PI or appropriate sub-investigator), date of resolution, seriousness, and outcome. AEs occurring during the study-collection and reporting period will be documented appropriately regardless of relationship.

AEs will be followed to resolution or stabilization.

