### Unsolicited Adverse Events

All AEs spontaneously reported by the participant and/or in response to an open question from study staff or revealed by observation, physical examination or other diagnostic procedures must be recorded on the appropriate DCF.

Unsolicited AEs of all severities will be reported from the time of study product administration through 28 days post each vaccination.

After 28 days post last vaccination through the end of study, only SAEs, AESIs (including PIMMCs, NOCMCs, and MAAEs), and AEs leading to withdrawal from the study will be reported.

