#### **Time Period and Frequency for Event Assessment and Follow-Up**

For this study, solicited adverse events will be collected for 7 days following each vaccine dose; unsolicited AEs will be collected until 28 days after each vaccination; AESIs (including PIMMCs, NOCMCs and MAAEs), SAEs, and AEs leading to withdrawal from the study will be collected from Day 1 through the end of the study. Clinical safety laboratory assessments are collected at Day 1 and 7 days post-vaccination for each dose.

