Review Memory Aid			X	X	X				X	X	X						X 	X 	
Adverse Events		X	X	X	X	X	X	X	X	X	X	X		X			X 	X 	
SAEs/AESIs including PIMMCs/MAAEs/ NOCMCs		X	X	X	X	X	X	X	X	X	X	X	X 	X	X	X	X	X	
Optional Leukapheresis 													X						
Saliva Collection for Antibodies		X			X							X							
Phone Call 			X	X						X									

 Includes WBC, HgB, PLT, ALT, AST, ALP, T Bili, CK, Cr and PT/PTT Includes WBC, HgB, PLT, ALT, AST, ALP, T Bili, CK, and Cr Safety lab per local Leukapheresis procedure If clinically indicated If within 7 days after study vaccination Includes SARS-CoV-2 serology (N-specific) only If prior to Study Visit 12 SAEs only Extra screening visit may be needed prior to Leukapheresis procedure Can be phone, text, or email contact

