## Implementation Notes:

For the Groups 5-15 tables, do not include the “At least one adverse event leading to treatment discontinuation” row, as those groups have only one study vaccination.]

Tables with similar format:

**Table 213: Overall Summary of Adverse Events by Vaccination Arm – COVID-19 Vaccination Naïve, 18-60 years of age, Groups 3B and 4**

**Table 214: Overall Summary of Adverse Events by Vaccination Arm – COVID-19 mRNA Vaccinated, 18-60 years of age, SAM-S-TCE Boosts**

**Table 215: Overall Summary of Adverse Events by Vaccination Arm – COVID-19 mRNA Vaccinated, >60 years of age, SAM-S-TCE Boosts**

**Table 216: Overall Summary of Adverse Events by Vaccination Arm – COVID-19 mRNA Vaccinated, >60 years of age, ChAd-S-TCE Boosts**

**Table 217: Adverse Events Occurring in 5% of Participants in Any Vaccination Arm by MedDRA System Organ Class and Preferred Term, and Vaccination Arm – COVID-19 Vaccination Naïve, 18-60 years of age, Groups 1 and 3A**

Preferred Term	MedDRA System Organ Class	Group 1: 5 x 10  vp ChAd-S/30 µg SAM-S (N=X)			Group 3A: 30 µg SAM-S/30 µg SAM-S (N=X)			All Participants (N=X)		
		n	%	Events	n	%	Events	n	%	Events
Serious Adverse Events										
All	All	x	x	x	x	x	x	x	x	x
PT1	SOC1	x	x	x	x	x	x	x	x	x
Etc.	Etc.									
Non-serious Adverse Events										
All	All	x	x	x	x	x	x	x	x	x
PT1	SOC1	x	x	x	x	x	x	x	x	x
Etc.	Etc.									
Solicited Adverse Events										
All	All	x	x	x	x	x	x	x	x	x
PT1	SOC1	x	x	x	x	x	x	x	x	x
Etc.	Etc.									
Any Adverse Event										
All	All	x	x	x	x	x	x	x	x	x

N = number of participants in the Safety Population (number of participants at risk).

n = number of participants reporting event.

Events = total frequency of events reported.

Solicited events ongoing past Day 8 are included as unsolicited events.

Tables with Similar Format:

**Table 218:** Adverse Events Occurring in 5% of Participants in Any Vaccination Arm by MedDRA System Organ Class and Preferred Term, and Vaccination Arm – COVID-19 Vaccination Naïve, 18-60 years of age, Groups 3B and 4

**Table 219:** Adverse Events Occurring in 5% of Participants in Any Vaccination Arm by MedDRA System Organ Class and Preferred Term, and Vaccination Arm – COVID-19 mRNA Vaccinated, 18-60 years of age, SAM-S-TCE Boosts

**Table 220:** Adverse Events Occurring in 5% of Participants in Any Vaccination Arm by MedDRA System Organ Class and Preferred Term, and Vaccination Arm – COVID-19 mRNA Vaccinated, >60 years of age, SAM-S-TCE Boosts

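### Unsolicited AE tables have no onset window or dose split, so their percentages mix 28-day complete collection with selective collection to 12 months

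*SAP*

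**What the plan says.** Section 9.3 gives the inclusion rule for AE summaries: "All adverse events reported will be included in the summaries and analyses".

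Section 4.5 describes two collection regimes. In the first, "Unsolicited AEs of all severities will be reported from the time of study product administration through 28 days post each vaccination"; the subsection on time period and frequency repeats that "unsolicited AEs will be collected until 28 days after each vaccination". The second regime is narrower: "After 28 days post last vaccination through the end of study, only SAEs, AESIs (including PIMMCs, NOCMCs, and MAAEs), and AEs leading to withdrawal". Section 4.1 follows everyone for 12 months after the last dose, and the definition of a medically attended event in Section 4.5 covers any unscheduled medical contact, whatever the cause.

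Section 9.3.2 says unsolicited AEs will be summarised separately by dose and also across both doses. It takes as denominator those who received the vaccination, whereas Section 9.3 uses the whole population.

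In Appendix 1, Table 7 (Groups 3B and 4) marks the AE row at every visit from V01 to V11, including D57 and D85, and again at V12. For unscheduled and early-termination visits the row carries the footnote "If prior to Study Visit 12". The note under Table 217 adds: "Solicited events ongoing past Day 8 are included as unsolicited events".

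**The concern.** Safety is the primary objective, and these tables are how the study report will present it. A reader who sees a percentage of participants with an unsolicited AE in a vaccine trial with 28-day collection will take it as a 28-day figure. Under the rule in Section 9.3, a clinic visit for an unrelated complaint at month 10 counts towards it in the same way as an event on Day 3. Background illness over the long tail can then swamp what happened near vaccination. The outputs affected are the unsolicited rows of Tables 212-216, the non-serious block of Tables 217-221, and Tables 256-306.

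Three further gaps meet in the same tables: the by-dose summaries have no output, the all-AE period for Groups 3B/4 is not settled, and prolonged solicited reactions may enter the event totals twice.

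**Working it through.** **1. The plan's own day count.** Study day = dose interval + day after dose 2. Groups 1/3A: 28 + 366 = 394. Groups 3B/4: 84 + 366 = 450. Both agree with Section 4.4.7, so the same arithmetic can be used for the AE windows.

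**2. Length of complete AE collection.** Inputs are the dosing days in Section 4.4.5, the intervals in Table 2 and the 28-day rule in Section 4.5.

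| Cohort | Calculation | Days |
|---|---|---|
| Stage 2, single dose | 28 | 28 |
| Groups 1/3A | 28 + 28 | 56 (53 to 59 with the ±3-day visit window) |
| Groups 3B/4, text of Section 4.5 | 28 + 28 | 56 |
| Groups 3B/4, Table 7 read as continuous | 84 + 28 to 129 + 28 | 112 to 157 |

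The two readings for Groups 3B/4 differ because Section 4.5 gives 28 days after each vaccination, while Table 7 records AEs at D57, which lies outside both 28-day periods. The D85 mark proves nothing by itself, since that is the dose 2 visit.

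**3. Length of selective collection.** In a single-dose arm the last visit is Day 366, which is 365 days after vaccination. Selective collection therefore covers 365 − 28 = 337 days.

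**4. Effect of the late tail (illustration).** The documents give no background rates, so these are assumptions. Let p be the 28-day incidence of any unsolicited AE and m the rate of medically attended events per person-year afterwards, with constant rates and independence:

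P(at least one) = 1 − (1 − p) × exp(−m × 337/365)

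With p = 10%:
- m = 0.3: 1 − 0.90 × exp(−0.277) = 31.8%
- m = 0.6: 48.3%
- m = 1.0: 1 − 0.90 × exp(−0.923) = 64.3%

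With p = 20% the results are 39.4%, 54.0% and 68.2%. There is no vaccine effect after Day 28 in any of these figures.

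**5. Effect of window length across cohorts (illustration).** With a constant rate, P = 1 − (1 − p)^(days/28):

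| 28-day incidence (assumed) | 56 days | 112 days | 157 days |
|---|---|---|---|
| 5% | 9.8% | 18.5% | 25.0% |
| 10% | 19.0% | 34.4% | 44.6% |
| 30% | 51.0% | 76.0% | 86.5% |

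**6. By-dose output.** The maximum-severity tables for solicited events in the two-dose groups come in Dose 1, Dose 2 and Any Dose versions (Tables 222-227). Tables 256-306 have one version per group and one pooled per cohort, with no dose columns. For Groups 1, 3A, 3B and 4 the summary described in Section 9.3.2 therefore has no shell.

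**7. Prolonged solicited reactions.** Table 231 already has a Day 8+ column for ongoing symptoms. Table 217 counts events in separate solicited and non-serious blocks, and its note moves prolonged reactions into the unsolicited count without saying whether they leave the solicited one.

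**The case against.** The strongest reply is that no planned AE table is unfair to any arm. Each shows one group or one cohort (1 and 3A; 3B and 4; 5 and 6; 9 to 11; 13 to 15), and the groups in a cohort follow the same schedule. No AE table sets Stage 1 beside Stage 2, and Section 6.8 rules out hypothesis testing. This stands. A reader might infer that incidence cannot be compared between the arms of a table, or that a longer-window arm will look less safe there; the shells do not support that. The only difference within a table is the individual 84 to 129 day dose interval in Groups 3B/4, which both arms are allowed equally.

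A reader might also take 112 to 157 days as the fixed all-AE period in Groups 3B/4. It is one of two readings. On the other, 56 days, those groups match Groups 1/3A.

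It can be argued too that Section 4.5 ties the 28-day window to unsolicited AEs, so tables titled as unsolicited are already limited. The wording leaves some room for this, but Section 9.3 sets no limit, Tables 256-272 are titled as covering all adverse events, Section 4.5 divides AEs only into solicited and unsolicited, and Section 9.3.2 lists AESIs and medically attended events under unsolicited AEs. A programmer following the SAP would include the late events.

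Some mitigation is already planned. Table 212 has separate rows for serious, medically attended and new chronic events, Tables 256-306 separate related from unrelated events, and Listing 11 gives days after dose. None of this removes late events from the unsolicited rows, and AESIs and PIMMCs have listings but no participant counts.

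Double counting of prolonged solicited reactions is a possibility, not something the SAP states. Section 9.3 counts a participant once for incidence, so the exposure is in event totals.

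**Conclusion.** The point holds for what the percentages mean, not for the comparison of arms within a table. As written, unsolicited AE percentages combine 28 days of complete collection per dose with selective collection to 12 months after the last dose. They cannot be read as post-vaccination incidence or set against another cohort's.

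Under the stated assumptions, a 10% 28-day incidence in a single-dose arm would be reported as 32% to 64%. Across cohorts, window length alone turns 10% into 19% at 56 days, and into 34% to 45% if Groups 3B/4 are collected continuously. The background rates are assumed; the window lengths, the missing onset limit and the missing dose split come from the SAP itself. The contradiction between Section 4.5 and Table 7 needs a decision whichever period was intended. Because this is a primary safety output, the change should be made before the tables are programmed.

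**What to change.** - **Window and dose.** Define the unsolicited AE outputs as events with onset within 28 days after a dose. For Groups 1, 3A, 3B and 4, add columns for dose 1, dose 2 and either dose. Use recipients of that dose as denominator, and bring Section 9.3 into line with Section 9.3.2. Figures 654-663 should follow the same rule.
- **Long-term categories.** Tabulate SAEs, AESIs, PIMMCs, medically attended events, new chronic conditions and AEs leading to withdrawal over full follow-up in a separate table with participant counts. Keep the serious block of Tables 217-221 over full follow-up.
- **Groups 3B/4.** State whether complete AE collection runs between the doses, reconcile Section 4.5 with Table 7, and show separately any event with onset more than 28 days after dose 1 and before dose 2.
- **Prolonged solicited reactions.** State that a solicited reaction continuing past Day 8 is counted once in event totals.

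Onset dates are already collected (Section 4.5), so the work is one onset-window flag. The cost is a few extra columns and one extra table.

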## 6. GENERAL STATISTICAL CONSIDERATIONS

### 6.1. General Principles

Unless otherwise noted, continuous variables will be summarized using the following descriptive statistics: n (non-missing sample size), mean, standard deviation, median, maximum and minimum. The frequency and percentages (based on the non-missing sample size) of observed levels will be reported for all categorical measures.

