### **6.3.3. Safety Population**

The safety population will consist of all participants who received at least one dose of a study vaccine. All analyses of safety data will be completed for the safety population.

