### 9.3.1. Solicited Events and Symptoms

Systemic solicited AEs were collected pre-vaccination, and systemic and local solicited AEs were collected 30 minutes post-vaccination and then daily for 7 days after each vaccination. Solicited local events include erythema (redness), induration (hardness)/edema (swelling), pain, and tenderness. Solicited systemic events include fever, chills (feverishness), fatigue (tiredness), malaise (general unwell feeling), myalgia (body aches/muscular pain exclusive of the injection site), arthralgia (joint pain exclusive for the injection site), headache, nausea, and diarrhea. Solicited events were graded on a scale of none (absent), mild, moderate, and severe. Measurement values for erythema and induration (hardness)/edema (swelling) were collected and graded based on the FDA Toxicity Grading Scale for Healthy Adult and Adolescent Volunteers Enrolled in Preventative Vaccine Clinical Trials [[4](#)].

Solicited AEs are summarized by severity pre-vaccination (systemic solicited AEs only), post-vaccination, and each day post-study vaccination (Days 1-8). Solicited AEs are also summarized by the maximum severity over all post-vaccination measurements. The proportions of participants reporting each symptom, any local symptom, any systemic symptom, and any symptom are summarized by vaccination arm separately for each dose and both doses combined (where applicable). For each event the denominator is the number of participants with non-missing data for the event.

The following summaries for solicited adverse events are presented by maximum severity, vaccination (each dose separately and both doses combined, where applicable), and vaccination arm:

- Number and percentage of participants experiencing solicited events by symptom and maximum severity, for any symptom, local symptoms, and systemic symptoms (beginning with [Table 222](#) and ending with [Table 230](#))
- Number and percentage of participants experiencing any solicited event, any systemic event, any local symptom, and each symptom, by day and severity, for each vaccination (starting with [Table 231](#) and ending with [Table 250](#))

- Duration of solicited symptoms summarized by mean, standard deviation, median, minimum, and maximum by symptom, dose, and vaccination arm ([Table 251](#), [Table 252](#), [Table 253](#), [Table 254](#), and [Table 255](#))

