## 14.3 Safety Data

### 14.3.1 Displays of Adverse Events

**Table 212: Overall Summary of Adverse Events by Vaccination Arm – COVID-19 Vaccination Naïve, 18-60 years of age, Groups 1 and 3A**

Participants a with		Group 1: $5 \times 10^{10}$ vp ChAd-S/30 µg SAM-S (N=X)		Group 3A: 30 µg SAM-S/30 µg SAM-S (N=X)		All Participants (N=X)	
Category 1	Category 2	n	%	n	%	n	%
At least one local solicited adverse event	NA						
At least one systemic solicited adverse event	NA						
At least one unsolicited adverse event	NA						
At least one related unsolicited adverse event	Any Grade						
	Mild (Grade 1)						
	Moderate (Grade 2)						
	Severe (Grade 3)						
At least one severe (Grade 3) unsolicited adverse event	Any relationship						
Related	Related						
Unrelated	Unrelated						
At least one serious adverse event b	Any relationship						
	Related						
At least one adverse event leading to early termination c	NA						
At least one adverse event leading to treatment discontinuation	NA						
Any laboratory Adverse Event	NA						

Participants a with		Group 1: $5 \times 10^{10}$ vp ChAd-S/30 µg SAM-S (N=X)		Group 3A: 30 µg SAM-S/30 µg SAM-S (N=X)		All Participants (N=X)	
Category 1	Category 2	n	%	n	%	n	%
Any Vital Signs Adverse Event	NA						
At least one medically attended adverse event	NA						
At least one new onset chronic medical condition	NA						

N = Number of participants in the Safety Population  
aParticipants are counted once for each category regardless of the number of events.  
bA listing of Serious Adverse Events is included in [Table 307](#).  
cAs reported on the Adverse Event eCRF.

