**Table 221:** Adverse Events Occurring in 5% of Participants in Any Vaccination Arm by MedDRA System Organ Class and Preferred Term, and Vaccination Arm – COVID-19 mRNA Vaccinated, >60 years of age, ChAd-S-TCE Boosts

**14.3.1.1      Solicited Adverse Events****Table 222: Number and Percentage of Participants Experiencing Solicited Events by Symptom, Maximum Severity, Dose, and Vaccination Arm - COVID-19 Vaccination Naïve, 18-60 years of age, Groups 1 and 3A – Dose 1**

		Group 1: 5 x 10  vp ChAd-S/30 µg SAM-S (N=X)		Group 3A: 30 µg SAM-S/30 µg SAM-S (N=X)		All Participants (N=X)	
Symptom	Severity	n	%	n	%	n	%
Any Symptom	None						
	Mild						
	Moderate						
	Severe						
Any Systemic Symptom	None						
	Mild						
	Moderate						
	Severe						
Arthralgia	None						
	Mild						
	Moderate						
	Severe						
Diarrhea	None						
	Mild						
	Moderate						
	Severe						
Fatigue	None						
	Mild						
	Moderate						
	Severe						

		Group 1: $5 \times 10^{10}$ vp ChAd-S/30 µg SAM-S (N=X)		Group 3A: 30 µg SAM-S/30 µg SAM-S (N=X)		All Participants (N=X)	
Symptom	Severity	n	%	n	%	n	%
Fever a	None						
	Mild						
	Moderate						
	Severe						
Feverishness	None						
	Mild						
	Moderate						
	Severe						
Headache	None						
	Mild						
	Moderate						
	Severe						
Malaise	None						
	Mild						
	Moderate						
	Severe						
Myalgia	None						
	Mild						
	Moderate						
	Severe						
Nausea	None						
	Mild						
	Moderate						
	Severe						

		Group 1: $5 \times 10^{10}$ vp ChAd-S/30 µg SAM-S (N=X)		Group 3A: 30 µg SAM-S/30 µg SAM-S (N=X)		All Participants (N=X)	
Symptom	Severity	n	%	n	%	n	%
Any Local Symptom	None						
	Mild						
	Moderate						
	Severe						
Erythema/Redness	None						
	Mild						
	Moderate						
	Severe						
Erythema/Redness Measurement (mm)	None						
	Mild						
	Moderate						
	Severe						
Induration/Swelling	None						
	Mild						
	Moderate						
	Severe						
Induration/Swelling Measurement (mm)	None						
	Mild						
	Moderate						
	Severe						
Pain	None						
	Mild						
	Moderate						
	Severe						

Severity is the maximum severity reported over all solicited symptoms post dosing for each participant.  
N=All participants receiving vaccination with any solicited event data recorded in the database.

Tables with similar format:

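### The SAP sets conflicting denominators for solicited-event percentages, so one symptom can be reported at different rates whenever a dosed participant lacks data

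*SAP*

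**What the plan says.** Safety is the primary endpoint (SAP Section 8.1), and Section 6.3.3 states that "All analyses of safety data will be completed for the safety population". Within that frame the SAP gives several bases for solicited-event percentages.

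- **Section 9.3**, which introduces Tables 212-221: for per-participant incidence, "the denominator will be the total population size".
- **Table 212** has rows such as "At least one local solicited adverse event" and its systemic counterpart, with "N = Number of participants in the Safety Population".
- **Table 217** has a solicited block by preferred term, with "N = number of participants in the Safety Population (number of participants at risk".
- **Section 9.3.1**, which introduces Tables 222-250: "For each event the denominator is the number of participants with non-missing data for the event". This agrees with the general rule in Section 6.1: "The frequency and percentages (based on the non-missing sample size) of observed levels will be reported for all categorical measures".
- **Table 222 footnote**, carried to Tables 223-230 as tables of similar format: "N=All participants receiving vaccination with any solicited event data recorded in the database".
- **Table 231 shell**, carried to Tables 232-250: 'Not Reported' is listed beside None, Mild, Moderate and Severe, under n and % columns. The N above each day's column is not defined in the footnotes.

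Section 9.3.2 separately bases unsolicited events on those who received the vaccination.

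**The concern.** A programmer who follows the document literally will divide the same solicited symptom by different numbers in different tables. The specific rule in Section 9.3.1 does not settle this by overriding the general one, because solicited events also appear in Tables 212-221, where the shells themselves fix the Safety Population as N.

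The groups hold 3 to 12 people, so one person in or out of the denominator shows in a whole-number percentage. A person without data who stays in the denominator is treated as if event-free, which lowers the reported reactogenicity. Readers of the study report would then find two rates for one symptom and nothing to say which was intended.

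**Working it through.** The SAP prints no figure that depends on this choice, so there is none to reproduce. The check sets the rules against each other and sizes the gap.

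**Inputs.** Group sizes from Table 2: 3 (Groups 3A and 4), 4 (Group 1), 7 (Group 3B), 10 (Groups 5 and 6), up to 12 (Groups 10 and 11). The SAP gives no missing rate, so the number missing, m, is an assumption: 0, 1 or 2.

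**Step 1: how many distinct rules.** By Section 6.3.3, the total population of Section 9.3 is the Safety Population, so those two are one. Three written definitions remain: Safety Population, non-missing for the event, and any solicited data recorded. The 'Not Reported' rows add an implied base that includes the missing.

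**Step 2: size.** With x reactors among N dosed and m without data, the two rates are x/N and x/(N − m). The gap is x·m / [N(N − m)]. For m = 0 it is zero. For m = 1, x runs from 1 to N − 1:

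| N | Smallest gap (x = 1) | Largest gap (x = N − 1) | Mid-range example |
|---|---|---|---|
| 3 | 1/6 = 16.7 points | 2/6 = 33.3 points | 1/3 = 33% vs 1/2 = 50% |
| 4 | 1/12 = 8.3 | 3/12 = 25.0 | 2/4 = 50% vs 2/3 = 67% |
| 7 | 1/42 = 2.4 | 6/42 = 14.3 | 3/7 = 43% vs 3/6 = 50% |
| 10 | 1/90 = 1.1 | 9/90 = 10.0 | 5/10 = 50% vs 5/9 = 56% |
| 12 | 1/132 = 0.8 | 11/132 = 8.3 | 6/12 = 50% vs 6/11 = 55% |

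For m = 2 the gap is 2.5-20.0 points at N = 10 and 1.7-16.7 at N = 12.

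**Step 3: a by-day table.** Take Group 3A (N = 3) on a day when one person has a mild symptom, one has none and one missed the diary entry. With all three in the base, None, Mild and 'Not Reported' are 1/3 each and sum to 100%. Under Section 9.3.1 the base is 2, so None and Mild are 50% each. A 'Not Reported' percentage on that base would be 1/2, for a total of 150%. The shell and the text cannot both be followed.

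**Step 4: a maximum-severity table.** Take Group 5 (N = 10), where everyone returned a diary, one person has no value for a given symptom and 5 report it. Table 219 (same format as Table 217) gives 5/10 = 50%. The footnote rule for Table 228 also gives 5/10, because that person has some solicited data. Section 9.3.1 gives 5/9 = 56%. The shell has no missing row, so on the footnote's N the severity rows would total 9/10 = 90%.

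**The case against.** The strongest reply is that Section 9.3 is only the general rule and its subsections refine it: 9.3.1 for solicited events, 9.3.2 for unsolicited. Solicited events are recorded in the clinic 30 minutes after dosing and then daily for 7 days. A dosed participant with no post-dose record at all for a symptom should therefore be uncommon, and Tables 212-221 may well agree with Tables 222-230. The 'Not Reported' rows display missing data openly and do not hide it.

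Much of this stands for the maximum-severity tables. It does not remove the conflict, because Tables 212 and 217 place solicited rows on the Safety Population in their own footnotes and the Table 222 footnote is not the 9.3.1 rule. Nor does it cover the by-day tables, where one missed diary day is enough.

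A reader might also infer that participants who never received dose 2 will be counted as event-free and so dilute the dose-2 reactogenicity rates. The document does not support that. Dose-specific solicited percentages appear only in Tables 222-250. Both rules that govern them, the one in Section 9.3.1 and the Table 222 footnote, leave out anyone not given that dose. Tables 212-221 have no dose columns. No planned table divides dose-2 solicited events by the total population.

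**Conclusion.** The contradiction is real, lies in the current text and touches the primary safety summaries. It is a fault of specification. It does not show that any rate will be wrong: the SAP states no missing rate, and with complete data all the rules give the same percentage. If one dosed participant lacks data, the gap is about 17-33 points at N = 3 and 1-10 points at N = 10. It is most likely to appear in the by-day tables (231-250).

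Two further readings go too far. The total population and the Safety Population are not two competing denominators. It also cannot be said that the tables will disagree, only that the rules allow it. The point should be corrected before programming because the correction is easy and disagreeing tables would be awkward to explain afterwards.

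**What to change.** 1. In Section 9.3, make the denominator sentence defer to Section 9.3.1 for solicited events and to Section 9.3.2 for unsolicited events.
2. In Section 9.3.1, state one solicited rule: participants who received the dose and have non-missing post-dose data for that symptom, or for that symptom on that day in the by-day tables. Where doses are combined, as in the any-dose tables and Tables 212-221, this means data after at least one dose.
3. Apply the rule to the solicited rows of Tables 212-221 and to the footnotes of Tables 222-250, and define the daily N in Tables 231-250.
4. In Tables 231-250, show 'Not Reported' as a count only, outside the percentage base.
5. Print the number with data beside each percentage.

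Tables 251-255 need no change: they summarise durations among participants who had the symptom. The cost is wording and footnotes, with no new data or analysis. Where data are missing, some percentages in Tables 212-221 and in the by-day tables will be higher than on the Safety Population base.
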